6.1.1.3 Subgroup Analyses

The primary analysis of primary endpoints will be conducted for two subgroups for the target population of main primary estimands. Subgroups are defined by BoNT pre-treatment status. Subjects will be distinguished on whether they have been treated with BoNT of any serotype prior to randomization at any time for any treatment indication or not (treatment naïve). Two-sided 95% Wilson CIs for proportions and 95% Mantel Haenszel CIs for stratum-adjusted differences in proportions with Mantel Haenszel test p-values will be provided for the three regions. ICEs will be handled as described in [Section 6.4.6](#).

The last three supplementary analyses described below in [Section 6.1.1.4](#) also constitute subgroup analyses. They will be performed for the three primary efficacy endpoints on subjects whose in-person attendance of the primary endpoint visit was not affected by COVID-19 pandemic. The target of estimation is specified in full detail in the definitions of three supplementary estimands (see [CCI](#) XXXXXXXXXX). The population attribute is a subset of the population defined in [Section 6.1](#) for main primary estimands. For more details see [Section 6.1.1.4](#).

CCI

CCI

6.1.2 Secondary Efficacy Endpoints and Estimands

Secondary efficacy endpoints and estimands for key secondary endpoints are described in [Section 5.1.2](#). Definitions of MAS-based key secondary estimands are provided in [CCI](#) and of the subject's GAIS-based key secondary estimand in [CCI](#). No estimands are defined for further secondary endpoints.

6.1.2.1 Key Secondary Efficacy Endpoints and Key Secondary Efficacy Estimands

[figure not shown]
Main estimators for key secondary estimands will be calculated for the target population of main key secondary estimands and ICEs will be handled as described in [Section 6.4.6](#).

Main estimators for main key secondary dichotomous MAS-based efficacy estimands ([Section 5.1.2](#)) correspond to main estimators for main primary estimands (see [Section 6.1.1.1](#)). Missing data will be imputed as described in [Section 6.1.1.1](#). For all three anatomical regions and for investigator's as well as subject's assessments on the MAS, stratum-adjusted differences in proportions for overall comparisons of treatment Group U versus Group P (reference) with corresponding 95% Mantel Haenszel CIs and Mantel-Haenszel test p-values will be calculated. Responder rates with two-sided 95% Wilson CIs will be provided as well.

Main estimator for the main key secondary estimand based on subject's GAIS (see [CCI](#)) will be analysis of covariance with factors treatment group and site, and mean of baseline MAS for HFL, GFL, and LCL at maximum contraction assessed by subject as covariate.

CCI

CCI

According to the definition of the key secondary estimand based on subject's GAIS CCI specific ICEs will be handled by applying the composite strategy. In these cases, missing subject's GAIS ratings or ratings of CCI (see Section 6.4.6 on ICEs), regardless of whether the GAIS score from subject assessment at Day 30 (V4) is available or whether it is missing for the respective subject.

Least squares (LS) means, standard error, and two-sided 95% CI per treatment group and LS mean treatment difference ("Group U" – "Group P") with associated two-sided 95% CI and t-Test p-value will be provided. The null hypothesis of this t-Test is that the LS mean treatment difference is zero.

A similar SAS code to the following statements will be employed for this analysis:

[figure not shown]
CCI

The resulting value will be rounded to two decimals.

Multiplicity adjustment strategy for comparisons of treatment groups U and P on key secondary endpoints is described in Section 6.4.3.

CCI

CCI

Results for Group G&H from any analyses will only be interpreted descriptively.

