12.4.1.2.1 Key secondary efficacy endpoints and key secondary efficacy estimands

Main estimators for main key secondary dichotomous MAS-based efficacy estimands correspond to main estimators for main primary estimands (see [Section 12.4.1.1](#)). For all three anatomical regions and for investigator's as well as subject's assessments on the MAS, stratum-adjusted differences in proportions for overall comparisons of treatment group U versus P (reference) with corresponding 95% Mantel Haenszel CIs and p-values will be provided.

Main estimator for the main key secondary estimand based on subject's GAIS CCI will be analysis of covariance with factors treatment group and site, and mean of baseline MAS for HFL, GFL, and LCL at maximum contraction assessed by subject as covariate. Missing data on subject's GAIS at Day 30 will be handled following the same conservative imputation strategy as defined for missing MAS data at Day 30 in the main estimator of main primary estimands (see [Section 12.4.1.1](#)).

Multiplicity adjustment strategy for comparisons of treatment groups U and P on key secondary endpoints is described in [Section 12.7.4.7](#).

Supplementary analyses of key secondary endpoints for all three regions will be performed using the same methods as described for supplementary analyses of primary endpoints on the FAS, the PPS and on observed cases in FAS and PPS (see [Section 12.4.1.1](#)).

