In conclusion, when randomizing 180 subjects to Group U and 90 subjects each to Groups G&H and P, the study will have at least 90% power to establish efficacy of NT 201 using a hierarchical procedure for comparisons of proportions of GFL-, HFL-, and LCL-responders between Groups U and P. Assuming that about 15% of subjects will not complete the MP period, the proposed sample size will result in more than 150 completed subjects in Group U in this study. This number of completed patients in this study is considered sufficient to support the overall safety profile of NT 201 for simultaneous treatment of UFL.

4 Analysis Sets

The following analysis sets are defined for the statistical analysis of this study:

Safety Evaluation Set (SES)

The SES is the subset of all subjects who were exposed to study medication at least once. Subjects in the SES analyses will be analyzed as treated.

Note: In the definition of the SES above, "as treated" relates to actual study treatment in MP.

Full Analysis Set (FAS)

The FAS will consist of all randomized subjects. Subjects in FAS analyses will be analyzed as randomized.

Per Protocol Set (PPS)

The PPS is the subset of subjects in the FAS without major protocol deviations. Major protocol deviations will be defined during the blinded data review meeting.

Note: Subject **CCI** was randomized twice and only treated after second randomization. According to ITT principle treatment group from first randomization **CCI** will be used for analyses based on the FAS or PPS. Apart from random group assignment, no data recorded for **CCI** will be analyzed. Data recorded for **CCI** (second randomization) will be included in any statistical analyses.

5 Endpoints and Main Estimands for Analysis

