6.1 Efficacy Endpoints and Efficacy Estimands

Primary and sensitivity analyses of primary efficacy endpoints (see [Section 6.1.1.1](#)) and confirmatory analyses of key secondary endpoints will be based on the target population of main primary and key secondary efficacy estimands (see [Section 5.1.1](#) and [Section 5.1.2](#), respectively). It is defined as "Male and female adults (18 years of age or older) with HFL, GFL, and LCL of moderate (score of 2) to severe (score of 3) intensity at maximum contraction as assessed by the investigator and the subject according to MAS, as randomized in this study: Subset of subjects randomized to UFL treatment group or to Placebo treatment group, grouped by randomized treatment assignment.". Further efficacy analyses will be based on the FAS if not otherwise specified. Statistical tests will be two-sided hypothesis tests for between treatment differences in general. Adequate descriptive statistics as specified at the beginning of [Section 6](#) above will be provided for all endpoints.

In case Visit 7/Visit 8 or Visit 12/Visit 13 is performed on same day MAS assessments from Visit 7/Visit 12 will be duplicated to be also analysed and listed at Visit 8/Visit 13.

[figure not shown]

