6.1.2.2 Further Secondary Endpoints

Similar analysis strategy by region as described for supplementary analysis of primary endpoints on observed cases in FAS/ PPS (see [Section 6.1.1.4](#)) will be applied for the further secondary dichotomous MAS-based efficacy endpoints defined for the MP. In particular, proportions of subjects with at least one-grade improvement in treatment groups U and P will be compared by stratum-adjusted and unadjusted differences in proportions with corresponding 95% Mantel Haenszel CIs and p-values. Moreover, 95% CIs for proportions and unadjusted difference in proportions will be provided.

Group G&H will only be considered for statistical analyses of MAS of the GFL and HFL regions but not of the LCL region. Analysis of stratum-adjusted and unadjusted differences in proportions will be performed separately for Group U vs. Group P, Group G&H vs. Group P, and Total NT 201 vs. Group P. For Group G&H, proportions with two-sided 95% Wilson CIs will be provided for all three regions, but difference in proportions compared to Group P only for GFL and HFL regions. For GFL and HFL regions, proportions will also be provided for Total NT 201.

GAIS as assessed by the investigator at Day 30 of the MP will be analyzed using analysis of covariance with factors treatment group and site, and mean of baseline MAS for HFL, GFL, and LCL at maximum contraction assessed by investigator as covariate (see [Section 6.1.2.1](#)). Comparisons will be made for Group U to Group P, Group G&H to Group P, and Total NT 201 to Group P. Two separate ANCOVAs, one for Group P, Group U and Group G&H and one for Group P and Total NT 201 (Group U and Group G&H pooled) will be conducted.

Results for all further secondary endpoints including any p-values and 95% CIs will only be interpreted descriptively. No type I error adjustment will be applied.

For further secondary endpoints only observed cases will be analyzed. Analyses will be provided for FAS and PPS.

CCI

CCI

CCI

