6.4.3 Multiple Comparisons/Multiplicity

The family-wise two-sided type I error level $\alpha = 0.05$ for comparisons of treatment groups U and P on the primary and key secondary endpoints will be controlled by a hierarchical test procedure based on two-sided tests with $\alpha = 0.05$.

The hierarchical procedure for primary analysis ([Section 6.1.1.1](#)) will be performed as described below. First, using the Mantel-Haenszel test of the null hypothesis that the common difference in response rates at Day 30 is zero, Group U versus Group P will be tested for superiority for proportion of GFL-responders, second for proportion of HFL-responders, and third for proportion of LCL-responders. The test procedure will stop once statistical significance could not be reached.

In case statistical significance can be established for all three primary efficacy endpoints, the procedure will proceed to key secondary endpoints ([Section 6.1.2.1](#)): As next steps, Mantel-Haenszel tests for superiority of Group U versus Group P will be conducted for proportion of subjects with a score of 0 (no) or 1 (mild) on MAS at maximum contraction as assessed by the *investigator* at Day 30 for GFL, then HFL and finally LCL anatomical region. Thereafter, Mantel-Haenszel tests for superiority of Group U versus Group P will be conducted for proportion of subjects with a score of 0 (no) or 1 (mild) on MAS at maximum contraction as assessed by the *subject* at Day 30 for GFL, then HFL and finally LCL anatomical region.

Finally, GAIS as assessed by the subject at Day 30 of MP will be tested as described in [Section 6.1.2.1](#).

The hierarchical test procedure will stop once statistical significance could not be reached.

For any other statistical tests on primary or key secondary endpoints (e.g. comparison of treatment groups G&H and P), no type I error adjustment will be performed. The same accounts for any statistical analyses of further secondary and other endpoints.

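### The readable plan gives the GAIS ANCOVAs no protection against unequal variances, so with 2:1 and 3:1 allocation their 95% CIs lose nominal coverage if GAIS spread differs materially between arms.

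*SAP*

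**What the plan says.** SAP 6.1.2.1 states that the main estimator for subject GAIS "will be analysis of covariance with factors treatment group and site, and mean of baseline MAS for HFL, GFL, and LCL", the baseline MAS being the subject's own rating at maximum contraction. Protocol 12.4.1.2.1 specifies the same model. The outputs are "Least squares (LS) means, standard error, and two-sided 95% CI per treatment group and LS mean treatment difference", with a 95% CI and a t-test p-value for the difference.

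The population is Groups U and P only (SAP 6.1): "Subset of subjects randomized to UFL treatment group or to Placebo treatment group, grouped by randomized treatment assignment". The group sizes are in SAP section 3: "when randomizing 180 subjects to Group U and 90 subjects each to Groups G&H and P". The GAIS model is therefore planned at 180 v 90. Subject GAIS is the tenth and last test in the hierarchy (SAP 6.4.3), after three primary and six MAS-based key secondary tests.

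Investigator GAIS is descriptive. SAP 6.1.2.2 plans "Two separate ANCOVAs, one for Group P, Group U and Group G&H and one for Group P and Total NT 201", that is 2:1:1 and, with the active arms pooled, 270 v 90.

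On the variance, the SAP says only "A similar SAS code to the following statements will be employed for this analysis", and the code itself is redacted. No readable sentence names a group-specific residual variance, a robust standard error or a Welch-type method. No GAIS SD, effect size or power is given.

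**The concern.** A conventional ANCOVA estimates one residual variance and applies it to every arm. GAIS is a bounded improvement rating. If the drug works, the two arms sit at different places on the scale, and equal spread would be a coincidence. The fixed values assigned under the composite strategy and the conservative imputation of missing GAIS can also change the spread differently by arm.

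With equal arms, the pooled variance still gives the right standard error for the difference. At 2:1 it does not, because Group U dominates the pooled estimate while the smaller placebo arm contributes more to the true variance of the difference. At stake is whether the reported 95% CI for an alpha-controlled endpoint, and the per-arm intervals beside it, have their stated coverage.

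**Working it through.** **The plan's own figure.** SAP section 3 gives 93% power for LCL responders (20% v 5%, one-sided Fisher's exact test at 2.5%). Exact enumeration at 180 v 90 gives 93.5%. This confirms the group sizes but has no bearing on GAIS.

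**Inputs.** From the documents: nU = 180, nP = 90 (SAP section 3), about 10 sites (Protocol 6.1), and a model with treatment, site and one covariate. Assumed: the SD ratio r = SD(U)/SD(P), varied from 0.5 to 2, with SD(P) set to 1.

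**Formula for the difference** (site and covariate terms ignored):

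- Pooled variance: s² = [(nU−1)r² + (nP−1)] / (nU+nP−2)
- SE ratio, model to true: q = √{ s²(1/nU + 1/nP) / (r²/nU + 1/nP) }
- Coverage ≈ 2Φ(t·q) − 1, with t = 1.969 on 270 − 12 = 258 df

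At r = 1.5: s² = (179×2.25 + 89)/268 = 1.835. The model variance is 1.835/60 = 0.03058 and the true variance is 2.25/180 + 1/90 = 0.02361. So q = √1.295 = 1.138, and coverage is 97.5%.

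At r = 0.5: s² = (179×0.25 + 89)/268 = 0.499. The model variance is 0.00832 and the true variance is 0.0125. So q = 0.816, and coverage is 89.2%.

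| r = SD U / SD P | SE ratio, 180:90 | Coverage |
|---|---|---|
| 0.5 | 0.816 | 89.2% |
| 0.67 | 0.880 | 91.7% |
| 0.8 | 0.929 | 93.3% |
| 0.9 | 0.965 | 94.3% |
| 1.0 | 1.000 | about 95% |
| 1.1 | 1.032 | 95.8% |
| 1.25 | 1.076 | 96.6% |
| 1.5 | 1.138 | 97.5% |
| 2.0 | 1.226 | 98.4% |

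At 135:135 the SE ratio is 1.000 in every row, so for the difference the unequal allocation is the cause.

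**Total NT 201 v P, 270:90.** The same formula gives q = 0.824 and coverage of about 89.5% at r = 0.67, and q = 1.216 and about 98% at r = 1.5. The three-arm 2:1:1 model was not calculated separately.

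**Per-arm LS means.** The CI width relative to its correct width is s/SD(arm).

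- At 180:90 and r = 1.5: √1.835/1.5 = 0.903 for U (coverage about 92%) and 1.355 for P (about 99%).
- At 180:90 and r = 0.67: s² = 0.632, giving 1.186 for U (about 98%) and 0.795 for P (about 88%).
- At 135:135 and r = 1.5: s² = (2.25 + 1)/2 = 1.625, giving 0.850 for U and 1.275 for P. Equal allocation does not remove this error.

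**Simulation of the planned model.** Treatment, 10 sites of 18 v 9 and a baseline covariate; integer GAIS from −3 to 3 (an assumed scale); 6,000 runs per scenario; coverage of the 95% CI for the difference:

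| SD U / SD P (assumed) | Pooled SE | HC3 SE |
|---|---|---|
| 0.96 / 0.58 | 97.6% | 95.0% |
| 0.89 / 0.77 | 96.5% | 95.8% |
| 0.82 / 0.86 | 94.8% | 95.5% |
| 0.75 / 0.95 | 92.9% | 95.4% |
| 0.59 / 1.05 | 90.6% | 95.8% |
| 0.86 / 0.86, no effect | 95.2% | 95.6% |

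In the five scenarios with an effect (about 1.7 grades, assumed), the mean t statistic was 15 to 17.

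**The case against.** The strongest objection is that the pooled variance is inferred. The SAS code that would show the procedure, the variance structure and the degrees of freedom is redacted, as are other blocks in SAP 6.1.2.1. A t-test on an LS-mean difference does not rule out robust or group-specific inference. This stands. A reader might infer that the plan commits to one variance, but the documents show only that the readable text offers nothing else.

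A reader might also infer that the CI is too narrow. The documents give no SDs and so do not fix the direction. If placebo subjects cluster near no change and treated subjects spread out, the CI is too wide, which is conservative. If conservative imputation and composite values are low scores, they would tend to widen the spread in Group U and push the same way. Undercoverage needs the larger spread in placebo, and a loss of more than about two points needs placebo to be roughly 1.3 times as variable. Small differences matter little: ratios of 0.9 to 1.1 move coverage by less than about one point.

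Nor do the documents support a reading that error control or the significance call is at risk. If the two GAIS distributions are identical, the variances are equal and type I error stays at 5%. Equal means with unequal spreads would disturb it, but nothing in the documents points to that case. With a large effect the decision would not change. GAIS is the last test, so nothing follows it, and the sample size does not rest on it. Investigator GAIS is descriptive only.

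What remains is the reported interval. An interval that is too wide misstates precision as much as one that is too narrow, and choosing the variance estimator after seeing the SDs would be post hoc.

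**Conclusion.** The point holds as a matter of reported precision, conditional on the redacted code being a standard ANCOVA. At 180:90, nominal 95% coverage of the U−P interval becomes about 97.5% if NT 201 is 1.5 times as variable as placebo, and about 89-92% if it is 0.5 to 0.67 times as variable. It stays close to nominal for ratios near 1. The effect is larger at 270:90. Per-arm LS-mean intervals are miscalibrated under unequal variances whatever the allocation, so the 2:1 ratio is not to blame for that part.

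These sizes rest on assumed SD ratios and, in the simulation, on an assumed seven-point scale. Neither the size nor the direction can be read from the documents. The nine earlier tests in the hierarchy are untouched. The change is worth making because it is nearly free and removes reliance on an assumption that a working drug is likely to break.

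**What to change.** In SAP 6.1.2.1 (subject GAIS) and 6.1.2.2 (investigator GAIS), add one sentence: standard errors, confidence intervals and p-values for the GAIS ANCOVAs, including the per-arm LS means, will be based on the HC3 heteroscedasticity-consistent variance. Keep the model, covariates, estimand and hierarchy. HC3 leaves the point estimate unchanged. If the redacted code already specifies a robust or group-specific variance, it is enough to say so in the text.

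Treatment-specific residual variances with Satterthwaite degrees of freedom are an alternative but not an equivalent: they reweight the fit and can change the point estimate. One of the two should be chosen in advance.

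The cost is one SAP sentence, a small code change and a negligible loss of efficiency if the variances turn out equal.

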6.1.2.2 Further Secondary Endpoints

Similar analysis strategy by region as described for supplementary analysis of primary endpoints on observed cases in FAS/ PPS (see [Section 6.1.1.4](#)) will be applied for the further secondary dichotomous MAS-based efficacy endpoints defined for the MP. In particular, proportions of subjects with at least one-grade improvement in treatment groups U and P will be compared by stratum-adjusted and unadjusted differences in proportions with corresponding 95% Mantel Haenszel CIs and p-values. Moreover, 95% CIs for proportions and unadjusted difference in proportions will be provided.

Group G&H will only be considered for statistical analyses of MAS of the GFL and HFL regions but not of the LCL region. Analysis of stratum-adjusted and unadjusted differences in proportions will be performed separately for Group U vs. Group P, Group G&H vs. Group P, and Total NT 201 vs. Group P. For Group G&H, proportions with two-sided 95% Wilson CIs will be provided for all three regions, but difference in proportions compared to Group P only for GFL and HFL regions. For GFL and HFL regions, proportions will also be provided for Total NT 201.

GAIS as assessed by the investigator at Day 30 of the MP will be analyzed using analysis of covariance with factors treatment group and site, and mean of baseline MAS for HFL, GFL, and LCL at maximum contraction assessed by investigator as covariate (see [Section 6.1.2.1](#)). Comparisons will be made for Group U to Group P, Group G&H to Group P, and Total NT 201 to Group P. Two separate ANCOVAs, one for Group P, Group U and Group G&H and one for Group P and Total NT 201 (Group U and Group G&H pooled) will be conducted.

Results for all further secondary endpoints including any p-values and 95% CIs will only be interpreted descriptively. No type I error adjustment will be applied.

For further secondary endpoints only observed cases will be analyzed. Analyses will be provided for FAS and PPS.

CCI

CCI

CCI

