5 STUDY OBJECTIVES

The primary objective of this study is to assess the efficacy of simultaneous intramuscular injections of NT 201 in subjects with moderate to severe UFL in comparison to placebo.

The secondary objectives are to assess efficacy and safety of simultaneous single and repeat-dose intramuscular injections of NT 201 in subjects with moderate to severe UFL.

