8.2 Treatments administered

In the MP (Cycle 1) subjects will be randomized to one of three treatment groups CCI

- In Group U, subjects will receive 20 U NT 201 in the GFL area, 20 U NT 201 in the HFL area, and 24 U NT 201 in the LCL area (12 U per side).
- In the G&H group, subjects will receive 20 U NT 201 in the GFL area, 20 U NT 201 in the HFL area, and placebo in the LCL area.

- In the P group, all three areas will be treated with placebo.

In the OLEX period (Cycles 2 and 3), all subjects will receive NT 201 in all three areas

CCI

Injections will be administered as described in [Section 8.1.1.2](#).

CCI

In case of a public health emergency further treatments may be halted or postponed.

8.2.1 **Methods of assigning subjects to treatment groups**

At baseline visit V2, subjects will be randomized 2:1:1 to one of the three treatment groups (Groups U, G&H, or P). Randomization will be done by using an IWRS. Randomization numbers and date of randomization will be recorded in the eCRF.

Randomization will be stratified by investigational site and will be in blocks of appropriate size. This will ensure an approximately equal ratio of treatment groups between sites. The block size will not be disclosed to investigators until the study is unblinded.

No other criteria for stratification of randomization will be applied.

If subjects are discontinued from the study during the MP, no replacement of subjects is planned.

8.2.2 ***Selection of doses in the study***

The choice of the doses per treatment area used in this study are justified by experience from prior studies performed with NT 201 ^{CCI}

^{CCI}

^{CCI} as well as by published results from clinical studies with other BoNTA- preparations.

^{CCI}

A placebo-controlled study with total doses of 64 U of BoNTA- injected in a comparable manner as planned in this study showed that this dose is safe and effective for the treatment of UFL [De Boulle 2018].

[figure not shown]
The doses chosen in this study are also in accordance with the treatment doses recommended in the labeling for ^{CCI}

^{CCI}

8.2.3 ***Selection and timing of doses for each subject***

In the MP (Cycle 1), subjects will be randomized to one of the three treatment groups as described in Section 8.2 ^{CCI} Treatment (NT 201 or placebo) will be administered at the baseline visit V2 according to the instructions detailed in Section 8.1.1.2 and the ^{CCI} in ^{CCI}

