12 STATISTICAL METHODS

This section describes the statistical analyses intended at the time of study planning. Further details on the statistical and analytical aspects will be presented in the SAP.

Any deviations from planned analyses, the reason(s) for such deviation(s), and all alternative or additional statistical analyses that may be performed before database close or unblinding, respectively, will be described in amendments to the clinical study protocol or the SAP. All deviations and/or alterations will be summarized in the clinical study report.

In case of a pandemic disease outbreak, e.g. new COVID-19 public health emergency, if on-site visits are not possible due to site closures, travel limitations, or other considerations if site personnel or trial subjects become infected, the following mitigations should be considered and assessed in an updated statistical analysis plan:

- Describe changes to planned and additional analyses due to the public health emergency. Thoroughly assess amount and patterns of missing values and sources of bias such as missing values and virtual instead of live assessments (if applicable).
- Include systematic identification of protocol deviations due to the public health emergency.
- Consider the need for involvement of an independent Data Monitoring Committee particularly if trial sample size changes are anticipated.

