- Proportion of subjects with at least one-grade improvement from baseline to Day 30 (Visit 4) of MP on MAS for GFL at maximum contraction as assessed by the investigator.
- Proportion of subjects with at least one-grade improvement from baseline to Day 30 (Visit 4) of MP on MAS for HFL at maximum contraction as assessed by the investigator.
- Proportion of subjects with at least one-grade improvement from baseline to Day 30 (Visit 4) of MP on MAS for both left and right LCL at maximum contraction as assessed by the investigator.
- GAIS as assessed by the investigator at Day 30 (Visit 4) of MP.

No estimands are defined for further secondary endpoints.

CCI

CCI

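### Does SAP 6.1.2.2 leave a gap by planning no site-adjusted Group U minus Group G&H difference for the further secondary LCL endpoint?

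*SAP*

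**What the plan says.** The endpoint is defined in SAP 5.1.2 as "at least one-grade improvement from baseline to Day 30 (Visit 4) of MP on MAS for both left and right LCL at maximum contraction", rated by the investigator. SAP 6.1.2.2 governs its analysis:

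- On Group G&H: "Group G&H will only be considered for statistical analyses of MAS of the GFL and HFL regions but not of the LCL region". Protocol 12.4.1.2.2 carries the same restriction, so SAP and protocol agree.
- Stratum-adjusted and unadjusted differences in proportions are to be "performed separately for Group U vs. Group P, Group G&H vs. Group P, and Total NT 201 vs. Group P".
- Group G&H is not dropped from the LCL tables. Its "proportions with two-sided 95% Wilson CIs will be provided for all three regions"; only its difference from Group P is limited to GFL and HFL.
- "For further secondary endpoints only observed cases will be analyzed", on FAS and PPS, and the results are descriptive without type I error adjustment.

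On treatment, Protocol 8.2 gives Group U 20 U in GFL, 20 U in HFL and 24 U in LCL. Group G&H receives the same 20 U in GFL, then "20 U NT 201 in the HFL area, and placebo in the LCL area". Protocol 8.1.1.1 requires equal injection volumes for active and placebo. Protocol 8.2.1 stratifies randomisation by site, in blocks, at 2:1:1. The primary objective in Protocol section 5 is to "assess the efficacy of simultaneous intramuscular injections of NT 201 in subjects with moderate to severe UFL in comparison to placebo".

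**The concern.** Groups U and P differ in all three areas. A U versus P difference on an LCL score therefore estimates the effect of the whole regimen on that score. It cannot by itself show how much comes from injecting the LCL area. U and G&H differ only in the LCL injections, so their randomised difference on LCL holds GFL and HFL treatment constant. A trial that has this arm, yet excludes it from LCL comparisons, seems to leave its most specific contrast unused.

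If treating the forehead and glabella changed LCL scores, or influenced the raters, U versus P could overstate what the LCL injections do, and the planned differences would not reveal it.

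**Working it through.** **1. The plan's own figure.** SAP section 3 states 93% power for LCL responders at 20% (U, n = 180) versus 5% (P, n = 90), by a one-sided Fisher exact test at 2.5%. Enumerating all tables gives 93.5%, so the figure reproduces. It concerns U versus P on the primary responder definition and does not depend on Group G&H.

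**2. Is the exclusion sensible?** For LCL, G&H versus P compares placebo with placebo in the area being scored. Total NT 201 versus P would pool subjects with active and with placebo LCL injections. Keeping G&H out of the placebo-referenced LCL contrasts is therefore coherent.

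**3. What can be formed from planned output?** The LCL proportions with confidence intervals are planned for U and for G&H. SAP section 6 adds absolute and percent frequencies, with percentages on the number of observed cases. From those counts, the crude difference is pU − pG and its 95% half-width is

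1.96 × √[pU(1 − pU)/nU + pG(1 − pG)/nG].

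The documents give no one-grade LCL rates, so only the maximum (both rates 50%) holds whatever the rates:

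- 180 v 90: 1.96 × √(0.25/180 + 0.25/90) = 12.7 points.
- 153 v 76 (the planned 15% loss over the main period, probably pessimistic for Day 30): 1.96 × √(0.25/153 + 0.25/76) = 13.8 points.

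At assumed rates of 70% v 20% the half-widths are 10.6 and 11.6 points. These bounds are for the FAS; the size of the PPS is not given.

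**4. What would site adjustment add?** The Mantel-Haenszel weight of site k is nUk × nGk/(nUk + nGk). If each site has exactly two U subjects per G&H subject, with mk in G&H, the weight is 2mk × mk/(3mk) = 2mk/3, which is proportional to site size. The weighted mean of the site differences is then Σ mk(pUk − pGk)/Σ mk. This equals the crude difference exactly.

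Departures come only from incomplete blocks and uneven loss. Simulation assumptions: 10 sites of unequal size, blocks of 4 with the last one incomplete, between-site SD of 0.5 on the logit scale, and 15% random loss. The block size and the rates are not in the documents.

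| Assumed rates, U v G&H | Mean gap, adjusted v crude | 95th percentile of gap | Half-width, adjusted (Mantel-Haenszel/Sato) | Half-width, crude |
|---|---|---|---|---|
| 70% v 20% | 0.6 points | 1.5 | 11.4 | 11.6 |
| 50% v 50% | 0.7 points | 1.8 | 13.3 | 13.6 |

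The average gap is about one twentieth of the half-width (0.6/11.4 and 0.7/13.3 are both 0.05). Adjustment narrows the interval by 0.2 to 0.3 points.

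**The case for a change.** The strongest case for adding the contrast is that it is randomised and blinded with matched volumes, and has the same planned group sizes as U versus P. It would cost a few table rows, no alpha and no subjects. A site-adjusted estimate cannot be rebuilt exactly from overall proportions, and a contrast specified before unblinding carries more weight than one assembled later. Protocol section 12 offers a route, since additional analyses "will be described in amendments to the clinical study protocol or the SAP".

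The facts in this stand: no visible passage plans U minus G&H, and the contrast would be informative about attribution. The inference that its absence is a weakness does not stand, for four reasons.

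- No visible objective asks for attribution by area, and the documents give no evidence that GFL or HFL injection changes LCL scores or ratings.
- Results for further secondary endpoints are descriptive in any case, so the distinction between a planned row and one derived from planned rows carries little weight.
- The added precision is negligible, as shown above.
- An addition to the SAP would also have to be reconciled with the identical sentence in Protocol 12.4.1.2.2, so it is not quite the free edit it appears to be.

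One uncertainty remains. SAP 6.1.1 brings Group G&H into the supplementary analyses of primary and key secondary endpoints. The supplementary analyses in SAP 6.1.1.4, parts of 6.1.2.1 and 6.1.2.2, and the discussion of control groups in Protocol 6.2 are redacted. Whether U versus G&H is planned there, or why it was left out, cannot be seen. Hidden text is no ground for calling the contrast missing from the plan.

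**Conclusion.** The concern does not hold. The plan compares simultaneous treatment with placebo, as its objective requires, and its restriction on Group G&H for LCL is coherent and consistent between protocol and SAP. A reader who wants U minus G&H on the one-grade LCL endpoint can obtain it, with a crude interval, from tables already planned.

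What is absent from the visible text is the site-adjusted version. It would be expected to move the estimate by 0.6 to 0.7 points on average and rarely by more than about 1.8, against an uncertainty of roughly 11 to 14 points either side. These figures rest on assumed one-grade rates (70% v 20% and 50% v 50%), assumed blocks of 4, random 15% loss and moderate between-site variation. Exact equality of crude and adjusted estimates under complete 2:1 balance within sites needs none of those assumptions. An extra descriptive row is a matter of preference, and nothing in the plan needs correcting.
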